g: Hematology including hemoglobin, WBC with differential, and platelet count.

h: Blood chemistry including sodium, potassium, BUN, glucose, ALT/AST, alkaline phosphatase, total protein, total bilirubin, albumin, creatinine, and calcium.

i: Pregnancy test; for women of childbearing potential, a negative pregnancy test (urine or serum) must be documented between Screening and first day of treatment on study. Must be documented prior to 1st dose of medication on study

j: EKG prior to initial dose of APR-246 and after infusion on day -11 of the lead in phase. EKG will be performed on day 1 and at end of infusion on day 4 of cycle 1 and then on day 1 evaluations of subsequent cycles.

Concurrent medications will not be captured on CRFs but will be reviewed with subjects in clinic at start of cycle visits to determine if they are reveal any new AEs or SAEs. For patients with documented CR or PR at disease assessment following cycle 3, hematology and blood chemistry assessments will be required for D1 of each subsequent cycle and more frequently per the discretion of the treating physician.

* All screening/baseline evaluations will be performed within 4 weeks prior to the start of APR-246 and azacitidine treatment. All assessments are to be performed on day 1 of each week. In the event that a visit or test cannot be scheduled on the exact visit day, a window of ± 7 working days is allowable.

**Bone marrow aspirate will be only be required for day #-10 in the phase 1b component of the trial. In the phase 2 component, bone marrow assessment completed within 1 month of signing consent will be accepted to fulfill screening requirement as long as it has been completed following the last MDS treatment (excluding ESAs) and there are unstained core biopsy or clot sections available for p53 immunohistochemistry.

***Lead-in phase will only be part of the Phase 1b portion of the study.

****Continuation Phase: After completing cycle 6 response assessments, subjects who have stable disease or better may continue treatment with APR-246 and azacitidine on 28 day cycles. Bone marrow biopsy and aspirate will be repeated after every 3 cycles. A CBC and CMP will be obtained at Day 1 of each cycle or more often per study investigator.

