14. MEASUREMENT OF EFFECT

Definitions: Response and progression will be assessed according to modified International Working Group (IWG) 2006 criteria³⁴ (Appendix B).

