- i. Duration of response defined as the time between achieving response and progression of disease.
- ii. OS at 8 months
- iii. Proportion of subjects achieving hematological improvement (HI), partial response (PR), complete response (CR), and/or marrow CR (mCR) by the IWG 2006 criteria (see appendix B)
- iv. Proportion of subjects who obtain a response as defined by IWG 2006 criteria with a baseline *TP53* VAF $\geq 20\%$ versus $< 20\%$ or high versus low nuclear p53 protein expression

- v. Correlation of *TP53* VAF with nuclear p53 protein expression as determined by IHC
- vi. Proportion of subjects who achieve $\geq 50\%$ reduction in *TP53* VAF.
- vii. Progression free survival (PFS) and OS in clonal responders ($\geq 50\%$ reduction in *TP53* VAF) versus non-responders
- viii. Profile expression of genes related to p53-mediated signal transduction before and after APR-246 treatment
- ix. Profile ROS production before and after APR-246 treatment
- x. AML transformation according to World Health Organization (WHO) criteria
- xi. OS
- xii. LFS
- xiii. Determine recurrent gene mutations in *ASXL1*, *BCOR*, *BRAF*, *CALR*, *CBL*, *CEBPA*, *CSF3R*, *DNMT3A*, *ETV6*, *EZH2*, *GATA2*, *GNAS*, *IDH1*, *IDH2*, *JAK2*, *KIT*, *KRAS*, *MPL*, *NF1*, *NPM1*, *NRAS*, *PDGFRA*, *PDGFRB*, *PHF6*, *PTPN11*, *RAD21*, *RUNX1*, *SETBP1*, *SF3B1*, *SMC1A*, *SMC3*, *SRSF2*, *STAG2*, *STAT3*, *STAT5b*, *TET2*, *TP53*, *U2AF1*, *WT1*, and *ZRSR2* at study entry and serially throughout treatment to assess changes in somatic mutation landscape.

Preliminary data on the above endpoints will prove to be very useful for further investigation of this protocol's treatment. Such data will be summarized appropriately in an exploratory fashion. Both point estimates and 95% confidence intervals will be reported, if feasible. Time-to-event endpoints such as OS and LFS will be summarized using the Kaplan-Meier product-limit method.

16. Laboratory Correlates

Unless otherwise specified, all laboratory correlates will be performed in the laboratory of [name] or at Genoptix medical laboratory.

1. Mutation analyses

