APPENDIX B

RESPONSE CRITERIA FOR SUBJECTS WITH MDS AND CMML ACCORDING IWG 2006 CRITERIA³⁴

ALTERING DISEASE NATURAL HISTORY	
Complete remission (CR)	Bone marrow: $\leq 5\%$ myeloblasts with normal maturation of all cell lines Persistent dysplasia will be noted Peripheral blood: Hemoglobin ≥ 11 g/dL Platelets $\geq 100 \times 10^9/L$ Neutrophils $\geq 1.0 \times 10^9/L$ Blasts 0%
Partial remission (PR)	All CR criteria if abnormal before treatment, except: Bone marrow blasts decreased by $\geq 50\%$ over pretreatment but still $> 5\%$ Cellularity and morphology not relevant
Marrow CR	Bone marrow: $\leq 5\%$ myeloblasts and decrease by $\geq 50\%$ over pretreatment Peripheral blood: if HI responses, they will be noted in addition to marrow CR
Stable disease (SD)	Failure to achieve at least PR, but no evidence of progression for > 8 weeks
Failure	Death during treatment Disease progression characterized by worsening of cytopenias, increase in % of bone marrow blasts, or progression to a more advanced MDS FAB subtype than pretreatment
Disease Progression (PD)	For subjects with: Less than 5% blasts: $\geq 50\%$ increase in blasts to $> 5\%$ blasts 5%-10% blasts: $\geq 50\%$ increase in blasts to $> 10\%$ blasts 10%-20% blasts: $\geq 50\%$ increase in blasts to $> 20\%$ blasts 20%-30% blasts: $\geq 50\%$ increase in blasts to $> 30\%$ blasts Any of the following: At least 50% decrement from maximum remission/response levels in granulocytes or platelets Reduction in hemoglobin (Hgb) concentration by ≥ 2 g/dL - Transfusion dependence
CYTOGENETIC RESPONSE	
Complete	Disappearance of the chromosomal abnormality without appearance of new ones
Partial	At least 50% reduction of the chromosomal abnormality
HEMATOLOGICAL IMPROVEMENT (HI)	
Erythroid response (HI-E) (Pretreatment < 11 g/dL)	Hgb increase by ≥ 1.5 g/dL Relevant reduction of units of RBC transfusions by an absolute number of at least 4 RBC transfusions/8 weeks compared with the pretreatment transfusion number in the previous 8 weeks. Only RBC transfusions given for a Hgb of ≤ 9.0 g/dL pretreatment will count in the RBC transfusion evaluation
Platelet response (HI-P) (Pretreatment $< 100 \times 10^9/L$)	Absolute increase of $\geq 30 \times 10^9/L$ for subjects starting with $> 20 \times 10^9/L$ Increase from $< 20 \times 10^9/L$ to $> 20 \times 10^9/L$ and by at least 100%
Neutrophil response (HI-N) (Pretreatment $< 1.0 \times 10^9/L$)	At least 100% increase and an absolute increase of $> 0.5 \times 10^9/L$

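### Appendix B lets a single blood count establish hematological improvement (HI), which can materially inflate the exploratory HI and overall response rates

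*Combined protocol and SAP*

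**What the plan says.** Section 14 sets the criteria: "Response and progression will be assessed according to modified International Working Group (IWG) 2006 criteria", with a pointer to Appendix B. The count-based HI rules there are:

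- HI-E, hemoglobin limb: "Hgb increase by" at least 1.5 g/dL (pretreatment below 11).
- HI-P: "Absolute increase of" at least 30 × 10⁹/L when starting above 20, or from below 20 to above 20 with at least a doubling (pretreatment below 100).
- HI-N: "At least 100% increase and an absolute increase of" more than 0.5 × 10⁹/L (pretreatment below 1.0).

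None of these has a duration. Two other rows of the table do. The transfusion limb of HI-E reads "Relevant reduction of units of RBC transfusions by an absolute number of at least 4 RBC transfusions/8 weeks", and stable disease reads "Failure to achieve at least PR, but no evidence of progression for" more than 8 weeks.

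HI is one of the categories in secondary endpoint iii (Section 15.4). Endpoint iv compares response by TP53 VAF and p53 expression, and endpoint i is duration of response. Section 10.3 lists HI among the responses. In Section 13, each scheduled hematology draw is described as "Hematology including hemoglobin, WBC with differential, and platelet count". Response assessment is marked only every 3 cycles and at end of treatment. Best response and date of first response are recorded.

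**The concern.** A rule that one value can satisfy, applied to a noisy measurement in up to three lineages and on several occasions, will be met by chance in some patients whose disease has not changed. The trial has a single arm, so no control rate shows how many of the HI responders are of this kind.

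Three secondary results are exposed. The HI and overall response rates rise. Responders by chance are unrelated to VAF or p53, so they pull any real difference between marker groups toward zero. If HI-only patients enter duration of response, some of the durations start from a fluctuation.

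**Working it through.** **1. The plan's own figures.** Section 15.1 continues at 6 or more CRs in 24 and declares success at 14 or more in 45. P(X ≤ 5 | n = 24, p = 0.20) = 0.656 (stated 0.66). P(success | 0.20) = 0.048 (stated 0.05). P(success | 0.40) = 0.900 (stated 90%). These reproduce. They use CR only, so HI does not enter.

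**2. Number of looks.** From the Section 13 calendar over six cycles: cycle 1 days 8, 15 and 22 give 3; cycles 2-6 on days 1, 8 and 15 give 5 × 3 = 15; C3D22 and C6D22 give 2; end of treatment gives 1. Total: 3 + 15 + 2 + 1 = 21 counts. The cycle 3 and cycle 6 assessments account for 2 of them.

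**3. One lineage, one look.** Take stable hemoglobin with an assumed within-patient SD of 0.7 g/dL and independent draws. The change from baseline has SD 0.7 × √2 = 0.99. Then P(change ≥ 1.5) = P(Z ≥ 1.5/0.99 = 1.515) ≈ 0.065. Two looks sharing one baseline give 0.112 by simulation.

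**4. Three lineages.** P(any HI) = 1 − (1 − a)(1 − b)(1 − c). At middle variability, two assessments and autocorrelation 0.5: 1 − 0.888 × 0.918 × 0.892 = 0.273 (simulated 0.272).

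**5. Simulation with no treatment effect.** All inputs are assumptions. Means are Hgb 9.0 g/dL, platelets 50 and ANC 0.6 (× 10⁹/L). There is one baseline draw, weekly autocorrelation from 0 to 0.8, six full cycles, and no transfusion or G-CSF.

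| Hgb SD / platelet CV / ANC CV | All 21 counts | C3D22 and C6D22 only | Held at every count over 8 weeks |
|---|---|---|---|
| 0.4 g/dL / 15% / 25% | 12-24% | 3% | 0-0.1% |
| 0.7 / 25% / 40% | 62-84% | 26-28% | 0.4-3% |
| 1.0 / 40% / 60% | 88-98% | 51-53% | 3-12% |

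Adding end of treatment as a third assessment gives 4-5%, 30-36% and 57-65%.

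A second set of assumptions (ANC 0.7; SD/CV of 0.5/20%/30%, 0.75/25%/40% and 1.0/30%/50%) gives 34-58%, 66-86% and 82-95% over all counts, and 12-13%, 30-32% and 45-47% at the two assessments. Requiring three consecutive day-1 counts cuts this to 0.2-11% over all scenarios of that set, including lower baselines (Hgb 8.5, platelets 30, ANC 0.5).

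**6. Sensitivity.** With only one eligible lineage, the first set gives 0.5-2%, 8-11% and 20-23% at the two assessments. With three lineages, autocorrelation 0.5, and baselines from platelets 30/ANC 0.4 to platelets 80/ANC 0.9, the span is 1-64% at two assessments and 6-96% over all counts.

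**7. Effect on the endpoints.** Let p be the real response rate and f the chance-HI rate among the rest. The observed rate is p + f(1 − p), and a difference between marker groups shrinks by the factor (1 − f) if f is equal in both. For illustration take p = 0.40 and f = 0.27, as if every non-responder were cytopenic in three lineages. The observed rate is 0.40 + 0.27 × 0.60 = 0.56, and a marker difference keeps 73% of its size.

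**The case against.** A reader might infer that, over some 20 counts, most patients with no treatment effect would be scored responders and that the response rate cannot discriminate. The documents do not support that.

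- The calendar labels only the 3-cycle and end-of-treatment visits as response assessments, and no text says an interim count may establish HI. On that reading the share passes 50% only at high assumed variability. This stands, but no text excludes interim counts either.
- Variability, baseline levels and cytopenia in all three lineages are assumed. Appendix C lists categories with fewer cytopenic lines, and eligibility requires no number of them. This stands; the figures are ranges, not estimates.
- The endpoint is exploratory, with no null rate, threshold or test. HI is a named category, while CR, PR and marrow CR need a marrow. This stands, so the claim is inflation only.
- The simulation has no early stops. Appendix B's progression rule of a hemoglobin fall of at least 2 g/dL also has no persistence, and 1-3%, 14-24% and 31-45% of stable patients meet it in the same kind of model (low, middle and high variability). Counts are also held constant mid-cycle, although Section 11 lists falls in neutrophils and platelets as expected azacitidine effects. Both points suggest the all-count figures run high.
- It is tempting to say that duration of response must be shortened. But endpoint i ends at progression, relapse after HI is a separate row, and the plan does not say that HI-only patients enter endpoint i. The effect is conditional.
- The cited criteria may contain a duration. That cannot be checked from the documents. Section 14 calls the criteria modified and points to Appendix B, so an unprinted condition cannot be assumed.

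**Conclusion.** The gap is real and should be closed. As printed, three of the HI limbs can be met by one count, and the plan leaves open which counts qualify. In stable patients cytopenic in three lineages, chance HI runs at about 3-53% on the narrower reading and about 12-98% if every count is used. It is lower with one cytopenic lineage. The width of these ranges comes from inputs the documents do not give. The direction does not depend on them: the rule can only add false responders, and even at two assessments with middle variability it adds roughly a quarter to a third in such patients. The HI and overall response rates can be materially inflated and the marker comparisons diluted; duration of response is affected only if HI-only patients are included. The transfusion limb, the stage 1 stop and the final CR decision are untouched.

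**What to change.** In Appendix B, for the hemoglobin limb of HI-E and for HI-P and HI-N:

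1. Require the rise to be maintained for at least 8 weeks, shown on three consecutive cycle day-1 counts and dated from the first. Two 28-day intervals make 56 days, the window the table already uses. Day-1 evaluations may be done up to 7 days early, so say that nominal visits are meant.
2. State which pretreatment value is the baseline.
3. State that counts raised by transfusion or short-term G-CSF do not establish HI, and how such counts are identified.
4. Use this definition in endpoints iii and iv, say whether HI-only patients enter endpoint i, and report the response rate with and without HI-only responders.
5. Say whether the mention of HI in Section 10.3 follows the same definition, so that the two sections agree.

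Cost: a few lines of text and a programming rule. Day-1 counts are already required in every cycle, including after CR or PR, and a transfusion log is kept. Section 13 says concurrent medications are not captured on CRFs, so G-CSF dates would need a field. The reported HI rate will be slightly lower, and patients who stop within 8 weeks of a first rise are not counted as HI. Within six cycles the possible runs are C2-C4, C3-C5 and C4-C6, so a rise first seen on day 1 of cycle 5 or later can be confirmed only if treatment continues.

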APPENDIX C: 2016 WHO CLASSIFICATION FOR CMML AND MDS³⁵
WHO CMML

WHO Subtype	Peripheral Blood	Bone Marrow
#Chronic Myelomonocytic Leukemia *CMML-0 **CMML-1 ***CMML-2	*<2% blasts **≥2% and <5% blasts ***≥5% and <20% blasts persistent monocytosis > 1 x 10 ⁹ /L and >10% of differential +/- cytopenias Leukocytosis frequent	* <5% blasts **≥5% and <10% blasts ***<20% blasts >10% dysplasia in affected lineage ***Auer Rods The absence of the Philadelphia chromosome of bcr-abl fusion gene.

[#]Not meeting WHO criteria for *BCR-ABL1* CML, PMF, PV, or ET. No evidence of *PDGFRA*, *PDGFRB*, or *FGFR1* rearrangement or *PCMI-JAK2* (should be specifically excluded in cases with eosinophilia). If myelodysplasia is absent or minimal, CMML diagnosis can be made with acquired clonal cytogenetic/molecular genetic abnormality or monocytosis x 3 months when all other causes of monocytosis have been excluded. Blasts and blast equivalents include myeloblasts, monoblasts, and promonocytes.

WHO MDS

WHO Category	Peripheral blood	Bone marrow
MDS with single lineage dysplasia (MDS-SLD)	Cytopenia (1-2 lines) <1% blasts	Dysplasia (1 line) < 5% blasts RS <15%/<5%†
MDS with ring sideroblasts (MDS-RS)*	Cytopenia (1-3 lines) < 1% blasts	Dysplasia (1-3 lines) < 5% blasts RS >15%/>5%†
MDS with multi-lineage dysplasia (MDS-MLD)	Cytopenia (1-3 lines) < 1%blasts	Dysplasia (2-3 lines) < 5% blasts RS <15%/<5%†
MDS with excess blasts type I & II (MDS-EB-1 & MDS-EB-2**)	Cytopenia (0-3 lines) Type I: 2-4% blasts Type II: 5-19% blasts	Dysplasia (1-3 lines) Type I 5-9% blasts Type II 10-19% blasts
MDS with isolated del(5q)***	Cytopenia (1-2 lines) < 1% blasts	Dysplasia (1-3 lines) < 5% blasts
MDS unclassified (MDS-U)****	Cytopenia (0-3 lines) 1% or < 1% blasts	Dysplasia (1-3 lines) < 5% blasts

Cytopenias defined as: hemoglobin < 10 g/dL; platelet count < 100 x 10⁹/L; and absolute neutrophil count < 1.8 x 10⁹/L. To be classified as dysplasia, >10% of any cell lineage must be dysplastic. PB monocytes must be < 1 X 10⁹/L. †If *SF3B1* mutation is present. *Subclassified as MDS-RS with single or multi-lineage dysplasia (MDS-RS-SLD or MDS-RS-MLD). Pancytopenia with RS is classified as MDS-RS-MLD. **Presence of Auer rods is classified as MDS-EB-2. *** Del(5q) alone or with 1 additional abnormality except -7 or del(7q). ****1% peripheral blasts needs to be confirmed on 2 separate occasions to make a diagnosis of MDS-U. MDS-U diagnosis is also made with SLD and pancytopenia or MDS defining cytogenetic abnormality in the absence of cytopenias.
